## **11.3 Serious Adverse Event (SAE) Reporting**

### **11.3.1 Study Center (Site) Requirements for Reporting SAEs**

Investigators and other site personnel must report any SAEs occurring during the course of the study within one business day of discovery of the event. This includes events both related and unrelated to the investigational product.

The definition of "related" being that there is a reasonable possibility the drug caused the adverse experience.

**Table 12: Relationship of adverse event to the investigational agent**

Unrelated	The Adverse Event is clearly not related to the investigational agent(s)
Unlikely	The Adverse Event is doubtfully related to the investigational agent(s)
Possible	The Adverse Event may be related to the investigational agent(s)
Probable	The Adverse Event is likely related to the investigational agent(s)
Definite	The Adverse Event is clearly related to the investigational agent(s)

**The completed SAE Report Form (see Study Procedure Manual) must be faxed to Hoosier Oncology Group within 1 business day of discovery of the event.** The investigator is responsible for informing the IRB and/or the Regulatory Authority of the SAE as per local requirements.

### **11.3.2 Death and Immediately Life-Threatening Events**

Any death and immediately life-threatening event from any cause while a patient is receiving trial treatment on this protocol or up to 30 days after the last dose of trial treatment, or any death and immediately life-threatening event occurring more than 30 days after trial treatment has ended but which is felt to be treatment related must be reported within one business day of discovery of the event. All deaths must be reported

primarily for the purposes of SAE reporting; however, deaths due unequivocally to progression are not SAEs.

Your local IRB should be notified and their reporting procedure followed. The completed SAE Reporting Form should be faxed to Hoosier Oncology Group **within one business day of discovery** of the event.

### **11.3.3 HOG Requirements for Reporting SAEs**

The Hoosier Oncology Group will report all SAEs that occur on subjects receiving rucaparib (from the time of first dose until 30 days post discontinuation) to Clovis within one business day of receipt of the SAE Reporting Form and to regulatory authorities (FDA) per federal guidelines.

The Hoosier Oncology Group will fax a MedWatch Report to:  
BioSoteria, Inc  
[contact] or [name]

### **11.4 IND Safety Reports Unrelated to This Trial**

IND safety reports not occurring on this trial but involving the study intervention (outside SAEs) received from outside sources will be reviewed by the Sponsor Investigator and will be forwarded to participating sites for submission to their Institutional Review Boards per their guidelines.

## **12.0 STATISTICAL CONSIDERATIONS**

**Table 13: Data Sets for Protocol Endpoints**

Data Set/Endpoint	Criteria
Disposition	All subjects registered into the study
General safety	All subjects receiving at least one dose of any drug
Efficacy	All subjects with at least one disease evaluation

Patients will be included in the analysis for the treatment to which they were randomized.

### **12.1 Sample Size Justification**

The primary endpoint for this trial is 2 year DFS. In order to detect an improvement of the fraction of patients free from disease at 2-year from 40% in the control arm to 63.2% in the rucaparib arm (corresponding to an HR=0.5), 38 events are needed to have 80% power to detect a difference in DFS using a one-side log-rank test with 0.10 level of significance (calculation done using nQuery Advisor 7.0 and assuming exponential survival). In order to observe 38 events we need to accrue about 102 patients, with an accrual time of about 13-18 months and an overall study duration around 25-30 months. In addition, 6 patients will be needed at the lower dose (cohort 1). Assuming ~20% will not be confirmed to have TNBC on central review; the total sample size will be increased to 135 to ensure 102 in the primary analysis (using cohort 2 and the randomized patients) and 6 in the safety analysis for cohort 1.

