## 2.0

### **OBJECTIVES**

#### 2.1

#### **Primary Objective:**

- To evaluate 2-year disease-free survival (DFS), in patients with confirmed TNBC or ER/PR + HER2-, known BRCA1/2 mutations treated with single agent cisplatin and patients treated with cisplatin in combination with rucaparib following preoperative chemotherapy

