## 8.0 CRITERIA FOR DISEASE EVALUATION

The primary efficacy endpoint of this trial is disease-free survival (DFS) in patients confirmed (by central testing) to have triple negative tumors or known BRCA1/2 mutation. DFS is defined as the duration of time from randomization to time of an DFS event, defined as local failure (invasive), regional failure, distant failure, contralateral breast cancer (invasive or non-invasive), any other second cancer (excluding non-melanomatous skin cancer or cervical cancer in situ), or death from any cause. The diagnosis of local or distant recurrence *should ideally be pathologically confirmed*, however if biopsy if not possible, radiology confirmation by CT, MRI, or PET scan is acceptable.

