## 12.4 Analysis of Primary Objective

The comparison of DFS between the two groups will be made using an unstratified Kaplan-Meier analysis with a log-rank test to test for differences using the patients in safety run-in cohort 2 and the randomized portion of the study. A specific comparison of 2-year DFS will be made using a two-sample test based on the complementary log-log transformation as suggested in Klein, et al. As supportive analysis, a stratified log-rank test will be done using the stratified randomization factors neoadjuvant anthracycline versus not and lymph node involvement at time of definitive surgery versus not. In addition, sensitivity analyses using Cox regression may be carried out to identify prognostic factors and provide adjusted estimates of the treatment group differences in DFS.

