## 12.5 Analysis of Secondary Objectives

As support for the primary objective, overall DFS and 2-year DFS will be compared using the same techniques above using only the subjects in the randomized part of the study. One-year DFS will be tested using the test described above for 2-year DFS. Safety and tolerability variables will be tabulated separately for the two groups. Incidences of selected adverse events from the two treatment arms may be compared using Fisher's Exact tests on an exploratory basis. OS will be compared between treatment groups using the same methodology as DFS. PK levels will be described using summary statistics. In addition, characteristics of tumor specimens, and genomic DNA will be correlated with PARP inhibition, recurrence and toxicity. Continuous measures will be correlated with binary variables (e.g. recurrence and toxicity) using maximal chi-

square tests and continuous variables (e.g. PARP inhibition) using Pearson or Spearman correlations. Binary variables such as tumor and genomic characteristics will be correlated recurrence and toxicity using chi-square or Fisher's Exact test. All of the analyses with the PK and correlative data are exploratory and are designed to complement efforts in other trials with this agent.

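### 2-year DFS is named primary, but the 38 events and 80% power belong to a log-rank test, and the plan does not say which test decides or when the 2-year test is run

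*Combined protocol and SAP*

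**What the plan says.** The primary objective (section 2.1 and the synopsis) is "To evaluate 2-year disease-free survival (DFS), in patients with confirmed TNBC" and in the other eligible group. Section 12.1 opens with "The primary endpoint for this trial is 2 year DFS".

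The sizing sentence that follows is for a different quantity: "38 events are needed to have 80% power to detect a difference in DFS using a one-side log-rank test" at the 0.10 level, assuming exponential survival with 40% v 63.2% disease-free at 2 years (HR 0.5). Section 8.0 defines the primary efficacy endpoint as time from randomization to a DFS event, with no 2-year landmark.

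Section 12.4, under the primary objective, gives two tests. The first is "The comparison of DFS between the two groups will be made using an unstratified Kaplan-Meier analysis with a log-rank test to test for differences". The second is "A specific comparison of 2-year DFS will be made using a two-sample test based on the complementary log-log transformation". Only the stratified log-rank test is called supportive there, and Cox regression is called a sensitivity analysis. Section 12.5 keeps the two comparisons separate and unranked: "overall DFS and 2-year DFS will be compared using the same techniques above using only the subjects in the randomized part of the study".

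The only timing is in section 12.1: about 102 patients, "with an accrual time of about 13-18 months and an overall study duration around 25-30 months". No section gives the 2-year test a significance level, a power or a data cut-off.

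**The concern.** A log-rank test compares the whole DFS curves. The complementary log-log test compares two Kaplan-Meier estimates at month 24. They are different tests with different data needs. The first is driven by the number of events, the second by how many patients are still at risk near month 24.

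The test that matches the named endpoint is therefore the one with no stated power, and the powered test is not specific to that endpoint. Two things are at stake:

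- **Choice of verdict.** If the tests disagree, either could be presented as the primary result once the data are known.
- **Timing.** If the 2-year test is run at the only date the plan mentions, most patients will not have reached month 24.

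**Working it through.** **Inputs.** From section 12.1: 40% v 63.2% at 24 months, HR 0.5, exponential survival, one-sided 0.10, 38 events, 102 patients, accrual 13-18 months, duration 25-30 months. Assumed: 1:1 allocation (section 12.3 expects about 20 per group among the first 40), uniform accrual, no dropout, and one-sided 0.10 for the 2-year test as well. A/T below means accrual/total months.

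**1. The plan's own figure reproduces.**
- HR = ln(0.632)/ln(0.40) = 0.501.
- Events = 4(1.2816 + 0.8416)²/(ln 0.5)² = 37.5, so 38. Power with 38 events is 80.4%.
- Expected events in 102 patients are 40.7 at 13/25 and about 44 at 18/30. The stated duration suits the log-rank target.

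**2. Follow-up at the stated dates.** The share of patients with 24 months of potential follow-up is (T − 24)/A:
- 13/25: 1/13 = 8%
- 18/25: 1/18 = 6%
- 18/30: 6/18 = 33%
- 13/30: 6/13 = 46%

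Expected at risk at month 24 is 51 × S(24) × that share. At 13/25 the control figure is 51 × 0.40 × 0.077 = 1.6. Everyone reaches 24 months of potential follow-up at month 13 + 24 = 37 or 18 + 24 = 42.

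**3. Large-sample power of the 2-year test.** The true difference on the complementary log-log scale is ln(0.9163/0.4589) = 0.692. The standard error (SE) comes from Greenwood's formula. Power = Φ(0.692/SE − 1.2816).

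| A/T | At risk at month 24, control v rucaparib | SE | Power |
|---|---|---|---|
| 13/25 | 1.6 v 2.5 | 0.436 | 62% |
| 18/30 | 6.8 v about 10.7 | 0.354 | 75% |
| 13/37 or 18/42 | 20.4 v about 32 | 0.299 | 85% |

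The other two pairings give 54% (18/25) and 81% (13/30).

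**4. Simulation (20,000 trials per scenario).** With so few at risk at 13/25 the large-sample value is rough, so the tests were also simulated.

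| A/T | Log-rank power | 2-year power | Tests disagree |
|---|---|---|---|
| 13/25 | 82% | 67% or 50% | 22% |
| 18/30 | 84% | 76% | 13% |
| 13/37 | 91% | 86% | about 8% |
| 18/42 | 92% | 86% | about 8% |

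At 13/25, about 27% of trials have an arm with nobody at risk at month 24. Power is 67% if the Kaplan-Meier curve is carried forward to month 24, and 50% if those trials count as failures. The 22% disagreement uses the carry-forward rule: 18% log-rank only, 4% 2-year only. Counting non-estimable trials as non-rejections, a separate run gave 37%.

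With an assumed 10% dropout by month 24, 2-year power is about 66% (45% with failures scored) at 13/25, 74% at 18/30 and 85% with mature follow-up.

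**5. Type I error if a claim could rest on either test.** With 40% in both arms and each test at one-sided 0.10, the chance of at least one rejection is about 14-16% at 13/25 and 14% at 18/30.

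**The case against.** The best reply is that the deciding test can be inferred. Section 12.1 uses the 2-year rates to express HR 0.5 and then powers a log-rank test, section 8.0 defines the endpoint as time to event, and section 12.4 lists the log-rank test first. It is the only test with a level, a power and an event count. On that reading, 2-year DFS is shorthand for the effect size. This is reasonable, but it is not written down, and the primary objective and the first sentence of section 12.1 point the other way.

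Second, the power loss depends on a date the plan does not set. The 25-30 months are tied to 38 events, and section 7.7 follows patients through year 5, so the 2-year test could be run later with 85-86% power. That stands: the low figures show what an unstated cut-off could cost, not a loss already built in.

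Third, 13/25 is the harsher case. The plan has no rule for non-estimable trials, so the 50% and 67% both rest on an added rule. At 18/30, equally within the stated range, the shortfall against 80% is 4-5 points. Some disagreement also remains with mature follow-up (about 8%), and most of it is log-rank only (about 11 of the 13 points at 18/30). These points limit the size of the problem but do not remove it.

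Fourth, no section proposes claiming success on either test, so the type I figures in step 5 are hypothetical and carry little weight.

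**Conclusion.** The concern holds and should be fixed. That no section names the deciding test, or dates and powers the 2-year comparison, follows from the text and needs no assumption.

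The sample size is not in error: 38 events give 80% log-rank power as stated. The size of the problem is a contingent range. If the 2-year test is run at the stated study end, its power is about 50-67% by simulation at 13/25 and 75-76% at 18/30, and the tests would give different verdicts in about 1 trial in 5 or 1 in 8. If it waits for mature follow-up, its power is 85-86%. These figures rest on 1:1 allocation, uniform accrual, exponential survival, no dropout and one-sided 0.10 for both tests.

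**What to change.** Name one deciding test and its trigger in sections 12.1 and 12.4, and align the synopsis, section 2.1 and section 8.0.

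**Preferred wording:** *The primary endpoint is DFS. The primary analysis is the unstratified log-rank test at one-sided 0.10, done at 38 DFS events in the primary analysis population. The comparison of 2-year DFS is secondary and is done once, when every patient in that population has at least 24 months of potential follow-up.*

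**Alternative:** keep 2-year DFS as primary, analyse it once at that later date (about months 37-42), make the log-rank test supportive, and restate power as about 85% and duration as about 37-42 months.

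Either wording needs the primary analysis population defined. Table 13 requires at least one disease evaluation, while section 8.0 requires central confirmation or a known BRCA1/2 mutation. Section 12.4 includes run-in cohort 2, whose patients have no randomization date from which to start DFS.

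**Cost:** protocol and SAP wording. The 2-year result is reported about 12 months after the stated study end (37 − 25 = 12; 42 − 30 = 12). Under the alternative, the primary result is delayed by the same amount. No patients or visits are added, because section 7.7 already follows patients through year 5.

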## 12.2 Patient Characteristics

Patient characteristics will be summarized by treatment group for demographics, baseline disease characteristics, and medical history. The two treatment groups will be compared using standard methods such as t-tests and chi-square tests.

## 12.3 Interim Safety Analyses

The first 12 patients (6 in cohort 1 and 6 in cohort 2) will be assigned to the rucaparib arm for an initial safety run-in. A safety analysis will be done after all six patients in each cohort have completed cycle 2. All toxicities will be tabulated. The study will move forward to cohort 2 if  $\leq 1$  of 6 in cohort 1 experience a DLT (as defined in Section 5.1). If  $\geq 2$  of 6 in cohort 1 experience a DLT, the study will be suspended and an amendment to explore alternate dosing schemes will be considered. Similarly, if  $\leq 1$  of 6 in cohort 2 experience a DLT (as defined in Section 5.1), the randomized portion will commence. If  $\geq 2$  of 6 in cohort 2 experience a DLT, the study will be suspended and an amendment to proceed with the randomized portion with the cohort 1 dose will be considered.

Once the decision is made to move forward with the randomized portion, a second safety analysis will be conducted after the first 40 patients (~20 from each group) have been randomized and completed 2 cycles of treatment. Toxicity counts and rates will be tabulated by treatment arm in a blinded fashion. The study will be terminated if the probability that the DLT rate equals 20% or less in either arm drops below .10. Accrual will continue during the interim analysis. The results of the analysis will be submitted to the CTMC for external review.

## 12.4 Analysis of Primary Objective

The comparison of DFS between the two groups will be made using an unstratified Kaplan-Meier analysis with a log-rank test to test for differences using the patients in safety run-in cohort 2 and the randomized portion of the study. A specific comparison of 2-year DFS will be made using a two-sample test based on the complementary log-log transformation as suggested in Klein, et al. As supportive analysis, a stratified log-rank test will be done using the stratified randomization factors neoadjuvant anthracycline versus not and lymph node involvement at time of definitive surgery versus not. In addition, sensitivity analyses using Cox regression may be carried out to identify prognostic factors and provide adjusted estimates of the treatment group differences in DFS.

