### 5.2.2 Randomization

During the randomized portion of the study, patients will be randomized to either Arm A or Arm B.

Stratification factors:

- Anthracycline vs. not
- Residual LN involvement vs. No Residual LN involvement

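### The primary DFS log-rank ignores both randomisation factors although its analysis set adds six non-randomised rucaparib patients; the stratified test, now only supportive, should be primary.

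*Combined protocol and SAP*

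**What the plan says.** Section 5.2.2 stratifies randomisation by two factors: prior anthracycline or not, and "Residual LN involvement vs. No Residual LN involvement". That makes four strata.

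Section 12.4 states that the primary DFS comparison "will be made using an unstratified Kaplan-Meier analysis with a log-rank test to test for differences". Its analysis set is run-in cohort 2 together with everyone randomised. The factors enter only afterwards: "As supportive analysis, a stratified log-rank test will be done using the stratified randomization factors". An adjusted Cox model is optional. The synopsis repeats this text.

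Section 12.3 says that the run-in patients, six per cohort, "will be assigned to the rucaparib arm for an initial safety run-in". Section 12.1 counts cohort 2 within the 102 patients of the primary analysis and sets the test: 38 events for 80% power "using a one-side log-rank test with 0.10 level of significance". Section 12.5 adds, as support, the same comparisons "using only the subjects in the randomized part of the study".

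**The concern.** Stratified randomisation balances the two factors between arms only among patients who were randomised. The six cohort 2 patients all sit in the rucaparib arm with whatever nodal and anthracycline profile they happen to have, and the primary test makes no allowance for it. Mostly node-negative patients would flatter rucaparib; mostly node-positive patients would handicap it.

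The protocol treats nodal status as important. It stratifies by it, section 3.10 makes residual nodal disease a route to eligibility, and section 1.1 cites a study whose title calls the size of residual nodal metastasis after neoadjuvant chemotherapy prognostic.

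At stake is how far a result from 38 events can be trusted once the nodal mix of the six is known, and which result governs if the unstratified and stratified tests disagree.

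**Working it through.** **The plan's own figure.** Inputs from section 12.1: one-sided 0.10, 80% power, 2-year DFS 40% v 63.2%, exponential DFS. Allocation is taken as 1:1, consistent with about 20 patients per group at the interim in section 12.3.

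- Hazard ratio: ln(0.632)/ln(0.40) = 0.501.
- Events (Schoenfeld): (1.2816 + 0.8416)² / (0.25 × (ln 0.5)²) = 4.508/0.1201 = 37.5, rounded up to 38. The stated figure reproduces.
- Power at 38 events: Φ(√(38 × 0.25) × 0.6931 − 1.2816) = Φ(0.855) = 80.4%.

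**Simulation.** 102 patients: the first six all on rucaparib, and 96 randomised 1:1 in permuted blocks of four within the four strata. Control 2-year DFS is 40% overall, treatment hazard ratio 1 (level) or 0.5 (power), with analysis at the 38th event. Not in the documents, and therefore assumed: nodal hazard ratio 1 to 3, 60% node-positive (varied below), 85% anthracycline use, block size, 18-month accrual. There were two independent programs, with 20,000 and 40,000 trials per scenario; Monte Carlo standard errors for the level are about 0.2 and 0.15 points.

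Results of the 40,000-trial program; each cell gives nodal HR 2 / nodal HR 3:

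| Node-positive among the six | Level, unstratified | Level, four strata | Power, unstratified | Power, four strata |
|---|---|---|---|---|
| 0 | 13.2 / 14.9% | 10.3 / 10.4% | 83.8 / 84.5% | 79.4 / 78.7% |
| 3 | 10.6 / 10.2% | 10.5 / 10.4% | 80.1 / 79.5% | 79.6 / 79.6% |
| 6 | 8.1 / 6.9% | 10.3 / 10.5% | 76.1 / 73.4% | 79.4 / 79.5% |
| Random mix | 9.9 / 9.5% | 10.3 / 10.2% | 79.3 / 77.7% | 79.4 / 79.1% |

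The 20,000-trial program adds the intermediate mixes:

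- Five of six node-positive: unstratified level 8.7–8.8% (HR 2) or 7.5–7.9% (HR 3). Power is 77.8–78.7% or 75.4–76.2%, against 79.7–80.6% stratified.
- Two of six node-positive: unstratified level 11.7–12.2%. In the other program, with analysis at 27 months (about 50 events) and HR 2, it was 11.0%.
- Four-strata level over all mixes: 10.0–11.1% (9.9–10.6% in the other program).
- Averaged over mixes: unstratified level 9.0–10.7%.
- Power with neither factor prognostic: 80.4% unstratified v 79.7% stratified.

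**How often the mix is uneven.** At 60% node-positive, the binomial chance of at most two of six is 0.0041 + 0.0369 + 0.1382 = 18%, and of at least five is 0.1866 + 0.0467 = 23%. Together that is 41%. The extremes are rare: 0.4% for none and 4.7% for all six.

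**Sensitivity to the node-positive share.** Unstratified level with five of six, then two of six, node-positive: 6.8–8.2% and 10.6–10.9% at a 50% share; 8.8–10.0% and 12.0–12.7% at a 70% share.

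**What stratifying does not cure.** Suppose the six differ from randomised patients within stratum (nodal HR 2, 60% node-positive). A run-in v randomised hazard ratio of 0.5 puts the stratified level at 12.9–16.0%; a ratio of 2.0 puts it at 5.3–6.7%. A stratified test on randomised patients alone stays at 9.7–10.4%, with power of about 77%.

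**The case against.** The unstratified test is not invalid. It holds its level on average, it was specified in advance, and it matches the sample-size calculation, which mentions no strata. The stratified and randomised-only analyses are already planned, so the change mostly swaps labels in a phase II trial tested at one-sided 10%. The harm needs a nodal effect that the documents do not quantify, and an uneven draw. The most likely draws, three or four of six node-positive, have a combined chance of 0.2765 + 0.3110 = 59% and leave the level near 10%. The power argument also runs both ways: a node-negative six raises unstratified power, though with an inflated level. Stratifying is not exact, since its level reached 11.1% in one scenario. Nor does it touch the larger weakness, that the six were not randomised.

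All of this is fair, and it limits the severity. It does not remove the point. The trial will be read with one known mix, not an average over mixes. Having the stratified test in support does not help if the two disagree, because the unstratified one governs. Differences within stratum are a reason to keep the randomised-only analysis, not to leave a measured imbalance uncorrected.

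**Conclusion.** The concern holds, as a recommended change and not a fatal flaw. Given an uneven nodal mix among the six, the primary test's level moves by about 1 to 3 points from 10%, and by up to about 5 or 6 points at the rare extremes (15.7% with none node-positive at a 60% share; 5.1% with all six node-positive at a 40% share and nodal HR 3). When the six are mostly node-positive, 2 to 4 points of power are lost at five of six. With a typical mix, or if nodal status is not prognostic, there is little or no distortion.

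Stratifying by both factors makes the level nearly independent of nodal mix. Confidence is medium, because the nodal hazard ratio, node-positive share and anthracycline share are all assumed. About 20% non-confirmation on central review would leave about 6 × 0.8 = 4.8 of the six, which shrinks the effect slightly. The separate 2-year DFS point comparison in section 12.4 is not part of this finding.

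**What to change.** In section 12.4 and the synopsis:

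- Make the log-rank stratified by the two randomisation factors the primary DFS test, and report a stratified Cox hazard ratio with it.
- State that both factors are recorded for the six cohort 2 patients. Sections 3.8 and 3.10 already require the prior regimen and the surgical pathology.
- Pre-specify a numeric collapsing rule that is blind to treatment. For example, stratify by nodal status alone if patients without anthracycline have fewer than 5 DFS events, both arms pooled.
- Keep the unstratified log-rank as a sensitivity analysis, and keep the randomised-only analysis of section 12.5 as a required check on the non-randomised six.

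The cost is wording only, with no new patients or procedures. Power falls by about 1 point if neither factor is prognostic; with a random mix it rises by about 1.5 points at nodal HR 3 (78.1% to 79.6% in the 20,000-trial program). In that program the example collapsing rule kept the level at 10.0–11.1% and power at 78.8–80.7%. It was triggered in about 0%, 30% and 96% of trials at 70%, 85% and 95% anthracycline use (10% and 88% at the latter two if the anthracycline hazard ratio is 0.6).
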